## Study Schema

## SUMMARY

The goals of this study are to study MMFS-202-302 in a double blind, randomized, placebo-controlled 9-week study of its effect on ameliorating cognitive deficits in 60 patients with schizophrenia or schizoaffective disorder with stable levels of positive symptoms. Secondary end points will include changes in functional measures, and positive and negative symptoms. One dose of MMFS-202-302 will be studied and compared with placebo as adjunctive treatment to atypical antipsychotic drug treatment. MMFS-202-302 is the clinical code describing the treatment formulation, combining the release profile of the compound and the dose of each tablet (i.e. 202 is a 0.5 g 6-hr release tablet and 303 is a 0.5 g 12-hr release tablet).

## 1.0 RATIONALE

### 1.1 Background and Significance

#### 1.1.1 Cognitive impairment in schizophrenia and schizoaffective disorder

Cognitive deficits of variable severity are present in virtually all patients with schizophrenia and schizoaffective disorder at the time of first diagnosis, are often the major reasons for functional impairment, and respond only partially to treatment with antipsychotic drugs (APDs) [1]. Even this is disputed by some authorities in the field, who attribute improvement to practice effects. However, it is indisputable that many patients can be shown to improve beyond a practice effect size in specific cognitive domains, especially semantic memory, declarative memory, and speeded motor testing [2-4]. Such improvement can be demonstrated in 6-12-week studies, with additional improvement over a six-month total study period. The search for agents which can be used to treat cognitive impairment in schizophrenia (CIS) is of the highest priority for these reasons.

Of particular note, working memory (WM) is a particularly impaired process demonstrated across the illness spectrum [5]. Of all clinical symptomatology experienced, negative symptoms (NS) have shown to be the most intractable, resilient to treatment, and debilitating with regards to functional outcome. Notably NS, which include alogia, blunted affect, asociality, avolition, and anhedonia, are somewhat associated with WM performance; however, the precise nature of this relationship is unclear [6]. Investigation of the reward system has proven particularly insightful in this regard, especially given that abnormalities in reward processing are relevant to different aspects of SCZ cognition as well as non-cognitive aspects of NS [7], particularly anhedonia and avolition [8]. Current research indicates differential areas of preserved and impaired function in aspects of reward processing in schizophrenia subjects, including valuation of hedonic experience, decision making, and rapid versus slow reinforcement learning [7]. Critically, this evidence also suggests WM is an influential intermediate variable in the production of abnormal hedonic experience and decision making in schizophrenia, noting that subjects with better WM show less severe deficits in these aspects of reward processing [9]. This suggests that previously believed dissociable WM and affective functions, subserved respectively by dorsal and orbital prefrontal and infralimbic cortices, are both implicated in deficit behavior related to schizophrenia. Given this relationship, it remains unclear whether this occurs as a result of faulty neural circuitry or abnormalities related to shared dopaminergic inputs, or both. Furthermore, there is strong evidence that the psychobiological substrates of negative symptomatology are directly related to both reward [10] and WM [11] circuitry. These circuits, and thus functions, are known to be heavily regulated by both mesocortical

dopamine (DA) D1, mesolimbic D2 receptors [10, 12], and prefrontal NMDA and GABAA and GABAB receptors [13]. From a pharmacologic perspective, this presents an opportunity for treatment using novel agents that act upon these receptors.

### **1.1.2 Preclinical Rationale for Studying L-Threonic acid Magnesium salt (L-TAMS; clinical code: MMFS) to treat CIS, negative symptoms, and possible adjunct for psychosis**

#### **Preclinical Evidence:**

L-threonic acid magnesium salt (L-TAMS - also known previously as magnesium L-threonate, MgT) has shown promise in PCP-induced animal models of schizophrenia as an adjuvant to clozapine in the amelioration of cognitive deficits [14]. It is hypothesized this occurs by L-TAMS enhancing the effectiveness of atypical antipsychotic NMDA and GABA actions, as Mg is a necessary co-factor in NMDA receptor response. In addition, recent data from [name] lab at Soochow University revealed that L-TAMS treatment improved PCP-induced social interaction in rats, an animal analogue widely studied model of NS. These promising findings prompt the investigation of this novel compound in the specific treatment of core cognitive and NS in schizophrenia, using both imaging modalities and clinical trial methodology. The value of these investigations is that precise neurobiological markers of potential change in NS can be identified.

Initial trials of putative cognitive enhancing drugs should collect data on all major domains of cognition, including working, semantic and episodic (declarative) memory, executive function, social cognition, attention and speed of processing as our knowledge in this area is limited. Findings from initial trials can then guide subsequent trials.

L-TAMS was also shown in a rodent study to improve novel object recognition (NOR) in subchronic phencyclidine-treated rats. This is a valuable model as a measure of declarative memory. Atypical APDs, including clozapine, have a similar effect on NOR in the PCP rodent model as we and others have shown. This model is based on NMDA hypofunction and dysfunction. They also improve other domains of cognition, including executive function and working memory. L-TAMS may do the same.

Mg2+ is a necessary co-factor in NMDA receptor response, and L-Threonate is a critical component of L-TAMS for delivery of Mg2+ to the CNS and to neurons. The basis for the effect of the atypicals is enhanced DA and ACh efflux in cortex and hippocampus as shown by studies with microdialysis. Electrophysiological studies show that the atypicals restore NMDA and GABA currents in cortex and hippocampus, respectively. Importantly too, L-TAMS has been shown to improve working memory in rats [14].

#### **Clinical Evidence:**

Recent studies have shown that L-TAMS (clinical code MMFS) can also improve cognition in humans, particularly frontal cortex-mediated executive functions such as working memory. In a double-blind, placebo-controlled human trial ( $n=50$ ), L-TAMS (MMFS-01) significantly improved *overall cognitive ability* in older adults with mild cognitive impairment (MCI) after 6 weeks of oral intake [15]. In that study, cognitive ability was assessed with a neuropsychological test battery (NTB; Cohen's  $d = 0.74, 0.91$  at 12 weeks), which was comprised of tests of working memory (Digit Span), executive function (trail making test – part B; TMT-B), episodic memory (Face-Name association test), and attention (Eriksen Flanker Congruent/Incongruent test). Notably, performance on the *Digit Span test* was significantly improved at 6 weeks by MMFS (Cohen's  $d = 0.61, p = 0.023$ ), and a trend remained evident at 12 weeks (Cohen's  $d = 0.30, p = 0.064$ ), indicating that L-TAMS can improve working memory in humans. The current study will help to inform our understanding of the generalizability of these procognitive effects to different patient populations, specifically schizophrenia and schizoaffective disorder.

### **1.1.3 Rationale for an RCT of Cognitive Effects of L-TAMS (MMFS-202-302) in Schizophrenia and Schizoaffective Disorder**

We propose to test the hypothesis that MMFS-202-302, the clinical formulation of the L-TAMS compound and dosage regimen, and a novel means to elevate intraneuronal Mg2+ levels in the brain, will improve one or more cognitive domains in patients with schizophrenia or schizoaffective disorder. This hypothesis is based upon data from [name] lab at Tsinghua University and [name] lab at Soochow University, that L-TAMS improves several

dimensions of cognition in rodents, particularly declarative memory as assessed by NOR and T-Maze, a measure of working memory. [name] reported that L-TAMS can augment the ability of sub-effective doses of the atypical APD clozapine to reverse the effects of subchronic PCP on NOR. We have found that other treatments which have a similar effect also improve other domains of cognition. We postulate that MMFS-202-302 will enhance the effectiveness of subeffective and/or clinical doses of other atypical APDs in addition to clozapine, as these drugs share many of the pharmacologic features of clozapine.

L-TAMS was also shown to improve PCP-induced social withdrawal, suggesting ability to improve negative symptoms. It blocked PCP-induced locomotor activity and impairment in PPI, suggesting ability to improve positive symptoms as well.

Patients receiving clozapine treatment will be favored for inclusion. L-TAMS has been shown to enhance the effect of clozapine to improve cognition and psychosis in PCP-treated rats. Patients receiving other atypical antipsychotic drugs that are widely used, i.e. risperidone, aripiprazole, quetiapine, lurasidone, or olanzapine will also be eligible. Patients with tardive dyskinesia will be excluded because of the evidence that tardive dyskinesia may indicate a treatment resistant form of cognitive impairment.

Additionally, this study will evaluate the potential WM enhancing and NS reduction effects of MMFS-202-302 among a group of individuals with schizophrenia disorder on a series of functional magnetic resonance imaging (fMRI) WM and reward tasks. We will evaluate whether MMFS-202-302 + APD vs. placebo + APD increases cognitive performance on a task of WM, and associated task-related increases in BOLD activation in the dorsolateral prefrontal cortex (DLPFC), and posterior parietal cortex (PPC). Additionally, we will assess whether MMFS-202-302 + APD vs. placebo + APD enhances reward circuitry (orbitomedial prefrontal cortex [OMPFC], anterior cingulate [ACC], nucleus accumbens [NAc], and ventral tegmental area [VTA]) and reward behaviors in the expression of NS. Positive findings will provide biomarker evidence for MMFS-202-302 effects on neural systems underlying these cognitive processes.

Finally, this study will measure brain network interactivity using electroencephalography (EEG) at baseline and end of study to examine any differences in activation or connectivity using learning and memory tests over the course of the trial. More information can be found in sections 5.0, 7.4, and 8.1 below.

## 2.0 OVERVIEW OF STUDY DESIGN

### Patient population

All patients will meet criteria for DSM-V diagnosis of schizophrenia or schizoaffective disorder. At the time of enrollment, they will have been receiving a stable dose of an atypical antipsychotic drug for 2 months or longer and have stable positive symptoms, i.e. delusions or auditory hallucinations, at the screening visit. 60 patients will be enrolled, and randomized in a 1:1 ratio to one dose of MMFS-202-302 or placebo.

### 2.1 STUDY OBJECTIVES

1. To determine the effectiveness of 9 weeks' supplementation with MMFS-202-302 as augmentation of atypical antipsychotic medication, to improve working memory or other specific domains of cognitive function, e.g. attention, executive function, declarative memory, etc., in patients with schizophrenia or schizoaffective disorder. The primary outcome measure will be a main effect of group on the 9-wk-change-from-baseline working memory subscale of the MATRICS Cognitive Consensus Battery (MCCB). The MCCB consists of 10 cognitive tests covering seven domains. This will be augmented by additional neuropsychological measures of verbal fluency (FAS Phonemic Fluency), working memory (Brown-Peterson's Auditory Consonant Trigrams) and executive function (the Wisconsin Card Sorting Test). The MCCB composite score, and each of the additional cognitive domain subscales listed above will be secondary outcome measures.
2. To determine the effect of MMFS-202-302 on global function, as measured by the Clinical

Global Impressions Scale (CGI) assessment of change (CGI-C).

3. To determine the effect of MMFS-202-302 on negative symptoms of schizophrenia, as measured by the Brief Negative Symptom Scale (BNSS) and PANSS negative subscale, and imaging of brain reward networks (OMPFC, ACC, NAc, VTA).
4. To determine the effect of MMFS-202-302 on positive symptoms of schizophrenia, as measured by the PANSS positive subscale.
5. To determine the effect of MMFS-202-302 as augmentation of atypical antipsychotic medication on both the behavioral performance and activation patterns in schizophrenia patients during a WM neuroimaging paradigm. Specifically, investigation in whether improvement from baseline task performance occurs for the MMFS-202-302 + APD group, and if this improvement is associated with increases in WM-related brain region activation (DLPFC & PPC).
6. To evaluate whether MMFS-202-302 results in greater functional connectivity within identified reward and working memory circuits in subjects with schizophrenia.
7. To determine whether MMFS-202-302 stimulates an overall enhancement or restoration of typical structural brain abnormalities in schizophrenia, as measured by cortical volume and thickness of the neocortex.
8. To examine the effect of MMFS-202-302 on neural connectivity and activation in EEG assessment, using measurements of learning and memory.

### **3.0 CRITERIA FOR EVALUATION**

#### **Primary Efficacy Endpoint**

- The primary efficacy endpoint will be the change from baseline to 9 weeks of MMFS treatment on the working memory MCCB subscale T-score, compared to placebo. The working memory subscale of the MCCB was selected as the primary outcome measure because working memory deficit is known to be a core feature of cognitive symptoms in schizophrenia and schizoaffective disorder patients, and contributes to deficits in other cognitive domains [16-18]. Our previous preclinical data [14] and clinical trial data with MMFS in mild cognitive impairment [15] demonstrate that MMFS is capable of improving working memory.

#### **Secondary Efficacy Endpoint**

- Clinical Global Impression of Change (CGI-C) – this clinician-administered interview is important for demonstrating that improvements in cognition correspond to an overall functional improvement - an FDA requirement for approval of a cognition-enhancing drug for schizophrenia patients.

#### **Tertiary/Exploratory Efficacy Endpoints**

- MCCB composite score – a common efficacy endpoint in trials of drugs for cognition enhancement in schizophrenia and schizoaffective disorder, providing evidence of global cognitive improvement.
- MCCB individual subscales and supplementary cognitive tests – these subscales and tests will provide additional information regarding the efficacy of MMFS for improving specific cognitive domains in patients with schizophrenia or schizoaffective disorder. We believe that MMFS may improve other aspects of cognition in addition to working memory, especially those that involve frontal cortex function.
- A working memory composite score derived from the two MCCB working memory subscale tests along with the Brown-Peterson's Auditory Consonant Trigrams test. Deriving a composite score from 3 working memory tests may be superior to the MCCB working memory subscale, which is a composite comprised of only 2 working memory tests. This possibility will be tested to identify the best composite measure of working memory for future trials.
- Responder analysis – the number of subjects achieving a clinical significance cutoff of improving at least one half of a standard deviation (T-score change  $\geq 5$ ) on the working memory subscale of the MCCB, to evaluate the clinical significance of any MMFS treatment effects; an analogous approach will be employed for secondary outcomes.
- Positive and negative symptoms – Positive symptoms will be assessed with the PANSS positive

scale, and negative symptoms will be assessed with the PANSS negative scale and the BNSS. We hypothesize that MMFS-202-302 may significantly improve negative and positive symptoms, at least partially independently from its cognition enhancing effects.

### **Exploratory Subgroup Efficacy Analyses**

Exploratory subgroup efficacy analyses will be carried out to inform enrichment of the study sample for future efficacy studies. MMFS is developed to improve cognition in patients with cognitive deficits, not as a general cognitive enhancer per se. Therefore, we plan to conduct subgroup analyses on the patients with cognitive deficits. Specifically, for the primary efficacy endpoint (MCCB working memory subscale), the data will be reanalyzed using ANCOVA as described above, restricted to the subgroup of subjects whose baseline score is at or below median for healthy age-matched norms (T-score of 50 or below on the working memory subscale). A similar analysis will be carried out using more conservative cutoffs of one half and one standard deviation (T-score of 45 and 40 or below), to further evaluate more severely deficient subsets of subjects. The purpose of these analyses is that we believe MMFS will be most efficacious for improving working memory in the subset of subjects who have working memory deficits upon entering the study. Analogous subgroup analyses will be carried out for the MCCB composite and other subscale scores, using the aforementioned cutoffs for the respective scores at baseline.

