## 8.0 STATISTICAL CONSIDERATIONS

### 8.1 Analysis of Clinical Data

Data will first be analyzed for efficacy on a per-protocol basis. The per-protocol population will include all subjects who complete all scheduled visits (+/- 5 days from planned visit time), have no protocol deviations that in the judgment of the principal investigator would invalidate their efficacy data, and achieve medication compliance of 80-120% (determined by pill counting; if pill packs are not available for confirmation, self-report of compliance will be used). Participants whose assessment falls +10 days or less from the scheduled visit will be included in per-protocol population, only if they were taking the study compound throughout. Data will secondarily be analyzed for efficacy on an intent-to-treat basis, with last observation carried forward (LOCF) for missing values or dropouts; subjects who did not receive any study compound will be excluded from the full analysis set, preserving the intent-to-treat principle. The primary analysis will be a univariate ANCOVA adjusting for baseline differences in the dependent measures of interest. We would also examine some variables categorically. The MATRICS working memory subscale T-score at 9 weeks will be the primary endpoint. Secondary endpoints will include the Clinical Global Impression of Change (CGI-C); the MCCB composite score; other individual cognitive domain subscale T-scores of the MCCB; a working memory composite score comprised of the 2 MCCB working memory subscale tests and the ACT test; and the PANSS positive and negative scales and BNSS. All endpoints will be evaluated as 9-weeks change from baseline, except for PANSS, which will be evaluated at both 6 and 9 weeks compared to baseline. Responder analyses will also be carried out using a chi-square test for the MCCB working memory subscale as a secondary endpoint evaluating clinical significance, using a cutoff of 0.5 standard deviation improvement (T-score improvement of  $\geq$  5 points). Finally, separate exploratory subgroup analyses will be performed on the MCCB working memory subscale T-score restricted to the subset of subjects who score 0, 0.5, or 1.0 SD or below the mean for normal age-matched normative data for that subscale. Analogous subgroup analyses will also be performed for the MCCB composite score, and the other MCCB subscale scores.

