Alpha will be set at 0.05 for all analyses. The individual scores for each of the 6 other neuropsychological MCB subscales, and supplementary cognitive tests (ACT, WCST, FAS), as well as the CGI-C measure of functional change will be evaluated to provide supporting information for primary and secondary measures.

Assumptions for the power analysis included random assignment into one group receiving placebo and one MMFS-202-302. The MCB, as the primary instrument will be collected at baseline and at end point (9 weeks). Using univariate ANCOVA with baseline score as covariate, the time average difference in the response variable will be compared between groups to detect treatment difference. Based on Javitt et al, 2012, we assume the mean baseline working memory score will be 36.4, SD 11.7 for both groups. We assume the placebo group will show no improvement with an SD of change of 6.5, while the treatment group will improve a mean of 5 points with the same SD of change, a medium effect. We assume the correlation coefficient of repeated observation to be 0.5 and the covariance structure to be compound symmetry. The power calculation was conducted with alpha level of 0.05. Full results are available upon request. With a two-sided test, the analysis reveals that 28 subjects per group are required assuming 5 points of improvement of the treatment group compared to the placebo for the desired power of 80% with alpha level of 0.05. We plan to recruit 30 per group to account for drop outs. Thus, allowing for attrition up to 20%, this sample size will provide 74-83% power to detect the hypothesized medium treatment effect.

We will assess MMFS-202-302 effects on negative and positive symptoms as additional endpoints, as measured by the BNSS and PANSS. Further, we will analyze the effect on drug tolerability as determined by the following: body weight, body mass index (BMI), waist circumference, and movement rating scales.

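### The low-baseline subset ANCOVAs estimate the effect in impaired patients but cannot show that it is larger there, which is what the enrichment question asks

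*Combined protocol and SAP*

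**What the plan says.** Section 3.0, under Exploratory Subgroup Efficacy Analyses, gives these analyses the purpose of guiding enrichment of future studies. It offers two reasons. One is that MMFS is meant for patients with cognitive deficits rather than as a general enhancer. The other is comparative: the authors expect the working memory benefit to be greatest in subjects who enter with a working memory deficit.

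The analysis itself is the same ANCOVA, "restricted to the subgroup of subjects whose baseline score is at or below median for healthy age-matched norms", meaning a working memory T-score of 50 or below. It is repeated at 45 or below and 40 or below, with analogous subsets for the MCCB composite and the other subscales. Section 8.1 repeats the plan: "separate exploratory subgroup analyses will be performed on the MCCB working memory subscale T-score restricted to the subset of subjects" at 0, 0.5 or 1.0 SD or more below the normative mean.

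The ANCOVA in Section 8.1 has baseline as a covariate only. No section plans a treatment-by-baseline interaction, an analysis of patients above a cut-off, or a comparison of effects across one.

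**The concern.** Whether MMFS works best in impaired patients is a question about the difference between two effects. A test within low scorers asks only whether there is an effect in low scorers. If the drug works equally at every baseline level, that test is still likely to be positive.

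The three subsets are also nested. For working memory, on the plan's own baseline values, the largest is nearly the whole trial, so it mostly repeats the main analysis with fewer patients. What is at stake is the design of the next trial: a restrictive entry criterion could be adopted on results that would look much the same with no differential effect.

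**Working it through.** **Inputs, all from Section 8.1 unless noted**
- Baseline: "we assume the mean baseline working memory score will be 36.4, SD 11.7 for both groups".
- Placebo: "no improvement with an SD of change of 6.5". Active: "the treatment group will improve a mean of 5 points with the same SD of change".
- Correlation of repeated observations: 0.5.
- Two-sided alpha 0.05; 30 per arm; attrition up to 20%, so 24 to 30 per arm.
- Cut-offs T = 50, 45 and 40 (Section 3.0).

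**1. The plan's own figure.** The plan states "With a two-sided test, the analysis reveals that 28 subjects per group are required" "for the desired power of 80% with alpha level of 0.05". A two-sample t-test on change, difference 5 and SD 6.5, has 80.7% power at 28 per group (79.2% at 27). It has 74.2% at 24 and 83.4% at 30, matching the plan's 74-83%. The plan gives no sample size or power for the subgroup analyses.

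**2. The planning values conflict.** SD 11.7 at both visits with correlation 0.5 implies an SD of change of 11.7 x sqrt(2 x (1 - 0.5)) = 11.7, not 6.5. An SD of change of 6.5 implies a correlation of 1 - 6.5^2/(2 x 11.7^2) = 0.846. Both correlations are carried forward as a range. The ANCOVA residual SD, 11.7 x sqrt(1 - r^2), is 6.2 at r = 0.846 and 10.1 at r = 0.5.

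**3. Subset sizes for working memory, assuming normality**

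| Cut-off | (cut-off - 36.4)/11.7 | Share at or below | Of 60 | Above |
|---|---|---|---|---|
| 50 | 1.162 | 88% | 53 | 7 |
| 45 | 0.735 | 77% | 46 | 14 |
| 40 | 0.308 | 62% | 37 | 23 |

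**4. Uniform 5-point effect, so no enrichment signal (simulated)**

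| Correlation | Per arm | T<=50 / 45 / 40 significant | At least one |
|---|---|---|---|
| 0.846 | 30 | 81 / 76 / 64% | 84-85% |
| 0.846 | 24 | - | 74% |
| 0.5 | 30 | 41 / 36 / 29% | 47-48% |
| 0.5 | 24 | - | 40% |

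The treatment-by-baseline test is significant in about 5%, its nominal rate, as it should be here.

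**5. Effect larger in less impaired patients** (+0.15 point of effect per baseline point, 5 at the mean). With 30 per arm and SD of change 6.5 or the matching correlation, at least one subset is still significant in 72-75% of trials. This is the favourable end of the inputs; it is 62% at 24 per arm with SD of change 6.5.

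**6. Comparing by eye is no remedy.** Under a uniform effect the T<=40 estimate exceeds the overall estimate in about half of trials.

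**7. What an interaction could show.** Splitting at a cut-off, SE = 2 x 6.5 x sqrt(1/n_low + 1/n_high). At T = 40: 13 x sqrt(1/37.3 + 1/22.7) = 3.46. The difference in effects detectable with 80% power is 2.80 x 3.46 = 9.7 points; likewise 11.2 at T = 45 and 14.3 at T = 50. If the effect is 5 below the cut-off and 0 above, power is 30%, 24% and 16% at T = 40, 45 and 50.

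For a continuous slope, SE = 2 x residual SD/(sqrt(N) x 11.7). Take a gradient of 0.15 per baseline point, or 1.5 points per 10:
- Residual SD 6.2, N = 60: SE = 0.14, power about 19%.
- Residual SD 10.1, N = 48: SE = 0.25, power about 9%.

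**The case against.** The strongest reply is that the restricted ANCOVA answers a legitimate question. Section 3.0 gives a non-comparative reason for it: patients with deficits are the intended population. Restricting both arms on a score taken before randomisation does not bias the comparison, and a later trial with a baseline cut-off needs exactly that stratum's effect and SD. This stands, and is why the refits should be kept.

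The analyses are also labelled exploratory, and no section says that a significant subset will trigger enrichment. That stands too, and it limits the weight of the point. It does not remove the mismatch, because guiding enrichment is the stated purpose and the comparative belief is written down.

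A third reply is that the interaction is too imprecise at this sample size to settle anything. Step 7 agrees. That argues for reporting an estimate with its interval rather than a pass/fail test; the width of the interval is itself useful to whoever designs the next trial.

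Four stronger readings are tempting, and the documents do not support them:
- A reader might take the 84-85% as a false-positive rate. It is ordinary power: with a uniform effect, a significant result in low scorers is a correct statement about low scorers. It is also the top of a range reaching down to about 40%.
- A reader might infer that the subsets are most of the trial for every score. Section 8.1 gives a baseline mean and SD for working memory only.
- A reader might add a multiplicity charge, since "Alpha will be set at 0.05 for all analyses". These analyses are declared exploratory, and with no drug effect at least one of the three working memory cuts is significant in only about 9% of simulated trials. An interaction term would not address multiplicity in any case.
- A reader might conclude that the trial's main result is at risk. The primary analysis does not depend on these subsets.

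**Conclusion.** The point holds in limited form. The plan voices a comparative hypothesis and has no analysis that tests it. A significant subset result cannot separate a drug that works better in impaired patients from one that works equally well in all, or even better in the less impaired.

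The size rests on assumptions that should be stated with it: normally distributed working memory scores with the planned mean and SD, equal SDs at both visits, a correlation of 0.5 (as stated) or 0.85 (as implied by the SD of change), and 24 to 30 analysed per arm. Actual subset sizes may differ. The logical point does not depend on these values. This is an inexpensive improvement to an exploratory analysis, not a defect in the primary one.

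**What to change.** For each score, add one exploratory ANCOVA in all analysed subjects with treatment, continuous baseline score and treatment x baseline. Report the interaction estimate with its 95% CI, and the model-based treatment effect with 95% CI at T = 40, 45 and 50.

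Keep the restricted ANCOVAs, described as estimates of the effect in the target population. State that no claim of a differential effect, and no recommendation to enrich, will rest on subset significance alone.

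The cost is one model term and a few sentences in Sections 3.0 and 8.1, with no new data or patients. The report should state the limits: the interaction is imprecise (about 9-19% power for a gradient of 1.5 points per 10 baseline points), it assumes linearity in baseline, and a non-significant interaction must not be read as showing no need to enrich.
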